This proposal will determine which training approach leads to the largest magnitude of improvement in neurocognition, functional capacity, and neural functioning measured with EEG. Moreover, it will shed light on the underlying mechanism of action associated with the observed improvements in cognition. Based on the neuroscience-guided theoretical framework described above, we expect that the effects of the bottom-up training 1) will result in robust changes in higher-order cognitive operations, 2) will be evident at the earliest stages of auditory processing (normalization of MMN), and 3) will generalize to functional capacity. We also expect that the bottom-up training will lead to superior effects on the primary and secondary outcomes relative to the top-down training. The proposed study will help to decide how best to implement CR interventions to improve the cognitive and social functioning of patients with schizophrenia. Subsequent studies could consider additional research questions, such as whether the benefits of training are maintained over time. Depending on the results of this study, treatment providers at the VAGLAHS will be able to decide which version of CR will lead to more substantial gains. Our prediction is that it will be the neuroplasticity-based intervention. However, this study will provide a clinically meaningful answer, even if our hypothesis is incorrect.

Preliminary Studies

Previous Work on Neurocognition in Schizophrenia

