bipolar patients, 30 schizophrenia patients, and 27 healthy controls during a duration-deviant oddball paradigm. We found impairments in both MMN and P3a in bipolar disorder (see Figure 3). At the earlier stage of automatic sensory discrimination reflected by MMN, bipolar patients showed deficits that were similar to patients with schizophrenia, but to a lesser degree. This finding suggests that both groups of patients may have problems detecting changes in their auditory environment. At the slightly later stage of orienting to salient auditory stimuli reflected by P3a, bipolar patients showed pronounced deficits, and these impairments were non-significantly larger than those in schizophrenia. This proposal will use the same auditory oddball paradigm, which has been tested in a large number of patients and healthy controls in our lab, to measure MMN and P3a.

Previous Work on Cognitive Remediation in Schizophrenia

I currently am lacking skills and experience in cognitive remediation with psychiatric patients, and I have identified this missing skill set as important to develop as part of my CDA training plan. [name] lab provides a conducive environment to filling that gap in my experience, given its long-standing research program focused on cognitive and social cognitive rehabilitation using both pharmacological and behavioral approaches. Moreover, the availability of local experts (Drs. [name], [name], and [name]) in addition to the identified co-mentor ([name]) will help me achieve my training goal.

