Subject recruitment will be coordinated through [name] ongoing studies. The availability of recruitment infrastructure, trained clinical interviewers, and cognitive remediation software will greatly facilitate the launch and conduct of the project. All subjects interested in the study will be prescreened for general inclusion and exclusion criteria by the recruiter using HIPAA compliant procedures. During the first visit (approximately 2 hours), participants will be consented and receive standardized clinical interviews to ensure diagnosis and eligibility. Participants will also receive symptom ratings of general psychiatric and negative symptoms, as well as mood symptoms. Subjects who fit selection criteria for the study will be scheduled for another visit, within 1 week of their first visit. During the second visit, (approximately 3.5 hours), subjects will be administered a comprehensive battery of cognitive, electrophysiological, and functional capacity/community functioning measures. Subjects will then be randomly assigned to one of the two cognitive remediation treatments (BFP and Cogpack) or to the control treatment (see randomization and treatment procedure below). Subjects will participate in 3 treatment sessions a week (1 hour each) for 12 weeks. After 18 treatment sessions, subjects will come back for a midpoint assessment visit (1.5 hours) in which they will be administered the electrophysiological measures again and two brief questionnaires. Upon completion of treatment, subjects will be scheduled for a post-treatment visit within 2 weeks of the last treatment session. This visit will last approximately 3.5 hours and will include the same clinical, cognitive, electrophysiological, and functional capacity/community functioning assessments that were administered prior to treatment. A urine toxicology screen will be conducted as part of each assessment visit. In the rare instance when a subject tests positive on the urine toxicology screen, he/she will be rescheduled to come back on a different day to complete the assessments. Overall, the study will consist of 4 visits (11 hours total) and 36 treatment sessions (36 hours total). Subjects will be compensated \$15/hour for the interview and testing sessions (first 2 visits, mid- and post-training visits) and \$10/hour for the treatment sessions, a rate deemed acceptable by our IRB. Funding is requested for four years of data collection (see Table 1). The IRB application will be prepared prior to the grant being funded.

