Data processing will be performed offline using BrainVision Analyzer 2 software (Brain Products, Gilching, Germany). Based on visual inspection, bad electrodes will be removed from the recording and a spherical spline interpolation will be used to recreate the electrode [52]. Data will be high-pass filtered at 1 Hz to remove slow drifts. Eye movement artifacts will be removed from the data using a regression-based algorithm [53]. Continuous data will then be divided into epochs relative to stimulus onset (-100 to 500 ms) and baseline corrected to the average of the prestimulus interval (-100 ms to 0). Only electrodes at frontocentral sites that are representative of neural activity generated by the MMN paradigm based on our previous studies (AF3, AF4, AF7, AF8, AFz, Cz, F1, F2, F3, F4, F5, F6, F7, F8, FC1, FC2, FC3, FC4, FC5, FC6, FCz, Fp1, Fp2, Fpz, Fz) will be examined. Following eyeblink correction, epochs that contain activity exceeding $\pm 75 \mu\text{V}$ at these electrode sites will be automatically rejected. Only data from subjects who have at least 100 acceptable deviant trials (out of 200) will be included in the analyses. MMN waveforms will be generated by subtracting ERP waveforms in response to standard tones from the ERPs generated in response to the deviant tones. The resultant MMN subtraction waveforms will then be low-pass filtered at 20 Hz (zerophase shift, 24 dB/octave rolloff) to remove any residual high-frequency artifact. MMN amplitude will be measured as the mean activity (expressed in μV) in the 135-205 ms latency range. This time window was chosen based on prior studies in schizophrenia [25]. Butterfly plots and 2-dimensional scalp topography of grand average MMN responses will be inspected to ensure that each subject is showing the expected pattern of activity (i.e., negativity at frontocentral regions and polarity inversion at the mastoids). Furthermore, only MMN responses that are at least 2 times the amplitude of any activity present in the 100 ms before stimulus onset will be considered valid [26]. The MMN amplitude at Fz will serve as the primary EEG outcome measure.

Behavioral Assessments

Neurocognition

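### The MMN validity rule depends on the size of the Aim 2 primary outcome itself; if failing recordings are left out, the BFP–Cogpack contrast can be modestly biased when the arms differ

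*Combined protocol and SAP*

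**What the plan says.** The EEG Processing section sets three checks on an MMN recording after artifact rejection.

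- **Trial count.** "Only data from subjects who have at least 100 acceptable deviant trials (out of 200) will be included in the analyses". This rule states its consequence and does not refer to the size of the MMN.
- **Visual check.** Butterfly plots and scalp maps "will be inspected to ensure that each subject is showing the expected pattern of activity". No consequence is stated.
- **Amplitude ratio.** The plan considers valid "only MMN responses that are at least 2 times the amplitude of any activity present in the 100 ms before stimulus onset". No consequence is stated here either.

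The sentence after the ratio rule reads: "The MMN amplitude at Fz will serve as the primary EEG outcome measure". The ratio rule is not limited to baseline. Research Design and Methods says that the post-treatment visit "will include the same clinical, cognitive, electrophysiological, and functional capacity/community functioning assessments that were administered prior to treatment".

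Under Primary Analyses, Aim 2 is tested by the group-by-time contrast between BFP and Cogpack in a mixed model with two time points. The plan describes that model as unbiased when data are missing at random. Attrition and Missing Data promises to use whatever was measured on every participant. It expects up to 20% loss from attrition and EEG artifacts together, and offers a propensity adjustment built from baseline variables if attrition looks selective.

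**The concern.** The ratio rule has the outcome on one side and pre-stimulus noise on the other. At a given noise level, a smaller MMN is more likely to fail. If training enlarges the MMN more in one arm, the other arm loses more recordings, and loses them from its low end. Its remaining mean then rises more, and the difference between arms changes.

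This loss depends on the endpoint value after allowing for baseline, so it is not missing at random. The mixed model's stated protection does not cover it, and a dropout model built from baseline variables cannot capture it. At stake is the comparison of main interest on one of three primary outcomes, in a study that says it is meant to supply effect estimates for a later definitive trial.

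The text also leaves open the site at which the rule is judged and whether amplitude is absolute or signed. Pre-stimulus activity is not defined either. Since epochs are "baseline corrected to the average of the prestimulus interval", its mean is zero by construction, so a peak or RMS measure must be intended.

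**Working it through.** **1. The plan's own figure.** Inputs from Power Considerations and Randomization and Treatment Procedure: 38 completers per active arm, r = .7, d = .5, two-sided α = .05.

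- SD of change = √(2 × (1 − .7)) = .775
- Standard error (SE) of the contrast = .775 × √(2/38) = .178
- Power = Φ(.50/.178 − 1.96) = Φ(.85) = 80%

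The claim of sufficient power, read as about 80%, is reproduced.

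**2. Dependence on the outcome.** A response of size y is valid if y ≥ 2N, where N is pre-stimulus activity. If N is half-normal with scale σ, P(valid | y) = 2Φ(y/2σ) − 1. With σ = .4 (in SDs of MMN, assumed):

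- y = 2: 2Φ(2.5) − 1 = 99%
- y = 1: 2Φ(1.25) − 1 = 79%
- y = 0.5: 2Φ(.625) − 1 = 47%

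**3. Effect on the contrast.** The documents give no MMN mean, SD, noise level or failure rate, so these are assumed over a range. Baseline and endpoint MMN are bivariate normal with SD 1 and r = .7. The true endpoint difference is .50, the same for everyone. Failing responses are dropped at both visits, and the group-by-time contrast is estimated by maximum likelihood in very large samples (simulation error about .005).

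| Reading of amplitude | Mean MMN (SD) | Noise scale | Endpoint failures, Cogpack / BFP | Contrast |
|---|---|---|---|---|
| absolute | 1.5 | .25 | 11% / 5% | .46 |
| absolute | 2.0 | .40 | 10% / 5% | .46 |
| absolute | 2.5 | .60 | 11% / 5% | .47 |
| signed | 1.5 | .10 | 9% / 3% | .44 |
| signed | 2.0 | .25 | 6% / 2% | .46 |
| signed | 2.5 | .40 | 5% / 2% | .48 |
| signed | 2.5 | .25 | 2% / 1% | .48 |
| signed | 2.5 | .10 | 1% / 0.2% | .49 |

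On the signed reading a response of the wrong polarity always fails; at a mean of 1.5 SD that alone is P(Z < −1.5) = 6.7%. Simulations with lognormal noise gave .43–.47 (signed) and .45–.48 (absolute) at 5–10% failing, and .48–.49 at 1–2%.

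**4. Size in standard errors.** (.50 − .43)/.178 = 0.39; (.50 − .48)/.178 = 0.11; (.50 − .49)/.178 = 0.06.

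**5. Do the planned remedies help?** The estimates in step 3 already come from the planned type of model. Weighting by baseline MMN and arm left .46–.47 in the three absolute-amplitude settings of the table, and .44 and .46 in two signed settings with about 11% failing.

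**6. Equal arms.** With no true difference and equal noise, the contrast was −.005 to +.004, that is, zero within simulation error.

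**7. Other effect patterns.** Signed reading, 5–10% failing, average effect still .50. Let the benefit be .5 × (1 + s·z), where z is the baseline MMN z-score.

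- s = −.6 (more benefit at small MMN): .37–.44
- s = .3: .48–.49
- s = .45: .50–.51
- s = .6: .52–.53
- benefit only above the median MMN: .53–.56

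**8. Power.** Signed reading, uniform difference of .50, rule failures counted inside the planned 20% loss: 78–81% at 1–2% failing and 73–80% at 5–10%, against about 80–81% with the same loss at random.

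**The case against.** The strongest objection is that the plan never says an invalid response leaves the analysis. The trial-count rule states its consequence and the ratio rule does not, while the missing-data section promises to use everything measured. That stands: the bias is conditional on exclusion. But a validity rule with no effect on the analysis would have no purpose, so exclusion is the natural reading, and at best the text allows two analyses of the same data.

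Second, a failing recording still has a measured amplitude. Unlike dropout, the exclusion can be reversed, and running the analysis both ways would show its effect. This also stands, and it is why the fix is cheap.

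Third, every input on size is assumed. Also true. The paradigm is one "which has been tested in a large number of patients and healthy controls in our lab", so the team may know its failure rate, but the documents do not give it.

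Three stronger readings are tempting and are not supported.

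- A reader might infer that the contrast is usually biased, and always toward zero. Background and Significance expects only that MMN will normalise. It does not say which patients would gain most, and step 7 shows patterns with no bias or with the opposite sign.
- A reader might infer that the rule can create a false difference. With equal arms and equal noise it does not. A false difference of .01–.05 at 5–10% failing needs something like 1.3-fold endpoint noise in one arm, and nothing in the documents suggests that.
- A reader might add rule failures to the planned 20% loss. The plan counts attrition and data loss together, so they belong inside it.

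The visual check is a lesser matter: it refers to grand-average responses and states no exclusion. The phrase about any pre-stimulus activity most naturally means the largest deflection, so that ambiguity is small.

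**Conclusion.** The concern holds in conditional form. The size of the Aim 2 primary outcome is part of its own validity test. If invalid responses are left out, endpoint loss depends on the endpoint MMN, and neither the mixed model nor the baseline-only adjustment repairs this. The BFP–Cogpack contrast can then be biased when the arms differ.

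Under a uniform shift and the assumed values, the shrinkage is 2–4% of the effect (.01–.02 of .50) at 1–2% failing and 4–14% (.02–.07 of .50) at 5–10% failing. It is smaller if amplitude is taken as absolute than if wrong-polarity responses fail. If benefit depends on baseline MMN, the bias may be larger, nil or reversed. There is no bias with equal arms and equal noise.

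The 100-trial rule does not have this problem. Severity is minor to should-fix: the effect is modest and its size unknown, but the rule as written gives a worse estimate than the alternative.

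**What to change.** Amend EEG Processing and the Aim 2 analysis text before arm-level EEG results are seen.

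1. In the primary Aim 2 model, analyse every recording that passes the existing artifact rejection and the 100-deviant-trial rule, whatever its MMN size.
2. Keep the 2-times rule only as a sensitivity analysis. State the electrode, the measure of pre-stimulus activity (peak or RMS), and whether amplitude is absolute or signed.
3. Report the number failing the rule by arm and visit.
4. State that the visual check of the response pattern does not exclude recordings from the primary analysis.

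An absolute limit on pre-stimulus noise is not a safe substitute in the primary analysis, because it can also depend on the outcome. With noise correlated .3–.7 with MMN, equal arms and 1.3-fold noise in BFP (all assumed), such a limit gave a false difference of −.03 to −.07, against about +.03 under the existing rule.

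The cost is wording, with no new data. A few noisier recordings stay in: in simulation, endpoint variance was 0–5% higher than with the noisiest 1–10% removed. The true figure depends on the unknown noise level.

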The experimental design for this study is a 3-group randomized clinical trial, with assessments at baseline and the 12-week treatment endpoint. The aims correspond to comparisons of the effects of two active treatments to each other and to a control condition on neurocognition, EEG, and functional capacity. For each of these domains, we specify a primary outcome measure. For neurocognition we will use a composite score created by averaging the t-scores for the 6 neurocognitive domains of the MCCB. The main EEG measure will consist of the MMN amplitude at electrode Fz. For functional capacity we will use the total score from the UPSA. If significant treatment effects are found on any of the primary outcomes, we will perform secondary analyses on the corresponding components or subscale scores to determine whether the results are driven by particular aspects of the main constructs. To further characterize the treatment response profiles, exploratory analyses will be performed to examine the effects of the interventions on composite scores of social cognition and community functioning. We are well aware of the risk of Type I error inherent in a study with a large battery of assessments and have protected against it by clearly specifying a limited a priori set of primary outcome measures and contrasts of interest and designating all others as exploratory. However, since this is a preliminary study, designed to obtain estimates of treatment effects and to identify optimal intervention components and measures for a future definitive efficacy study, it is equally important not to miss any potentially relevant outcomes. All results will therefore be reported using an uncorrected two-sided significance level of $\alpha=.05$.

Prior to performing the primary analyses, descriptive statistics and graphical summaries will be obtained for all outcomes to check for missing data, outliers and the need for transformations or non-parametric methods. To assess the success of randomization, ANOVAs and chi-square tests will be used to test for baseline group differences on the primary outcomes as well as on demographic (age, gender, parental/personal education) and clinical (medication, duration of illness, and symptom severity) characteristics. Measures that show significant differences will be included as covariates in subsequent analyses. Below we give a detailed description of the analytic plan by specific aim.

Analysis Plan By Specific Aim:

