Specific Aim #1: To compare the treatment effects of bottom-up training (BFP) to top-down training (Cogpack) as well as to a control condition on neurocognition.

Specific Aim #2: To compare the treatment effects of bottom-up training (BFP) to top-down training (Cogpack) as well as to a control condition on EEG (MMN).

Specific Aim #3: To compare the treatment effects of bottom-up training (BFP) to top-down training (Cogpack) as well as to a control condition on functional capacity.

Exploratory Aims: 1) To compare the treatment effects of bottom-up training (BFP) to top-down training (Cogpack) as well as to a control condition on social cognition and community functioning and 2) to assess whether changes in MMN are associated with changes in cognition and functioning.

Primary Analyses: To make the most efficient use of our data, our primary analytical technique will be the general linear mixed model (GLMM). GLMMs account for correlations induced by repeated measures within subjects, allow for both fixed and time-varying covariates and automatically handle missing data, producing unbiased parameter estimates provided that observations are missing at random. This allows us to include all available data from all subjects in the analyses, regardless of the degree of study participation or treatment dosage received, consistent with the intent to treat framework. For each of our primary outcomes (MCCB neurocognitive composite for Aim1, MMN amplitude at Fz for Aim 2, UPSA total score for Aim 3), our core model will include group (BFP, Cogpack, control) as the between subject factor, time (baseline, end of treatment) as the within subject factor, and a group by time interaction. Our primary hypotheses correspond to the group by time interactions comparing the outcome trajectories for the two active treatments, which can be obtained as post-hoc contrasts. Such contrasts can also be used to compare each of the active

treatments to the control condition, to test for within group change and to examine the magnitudes of group differences at the end of treatment.

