Exploratory Analyses: Significant results for the primary global measures will be followed by equivalent models for the component subdomain scores to identify the primary drivers of treatment effects. Parallel models will also be fit for the exploratory analyses of social cognition and community functioning measures. To examine the relationships between MMN and cognition and functioning, we will add this EEG index as a time-varying covariate to the primary GLMM models for the other outcome domains. Although we are underpowered for a full mediation analysis, this will also allow us to obtain a preliminary indication of whether treatment effects operate through their effect on electrophysiology. Given that age, duration of illness, symptom severity, medication (indexed by CPZ units) and dosage of treatment (number of sessions) may all impact treatment response, we will also add these measures and their interactions with treatment group and time to the primary models to (i) determine whether they explain additional variation in the outcomes and (ii) obtain preliminary information about potential treatment moderators.

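### Prespecify a baseline-adjusted primary analysis: the significance-triggered covariate rule has no stated form and, as main effects, would not correct the primary contrast

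*Combined protocol and SAP*

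**What the plan says.** Under Statistical Plan, "ANOVAs and chi-square tests will be used to test for baseline group differences on the primary outcomes", and also on age, gender, parental and personal education, medication, duration of illness and symptom severity. That makes 3 + 4 + 3 = 10 measures. The consequence is: "Measures that show significant differences will be included as covariates in subsequent analyses". Whether a covariate enters as a main effect or with a time interaction is not stated.

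Under Analysis Plan By Specific Aim (Primary Analyses), the core model has group as the between-subject factor, "time (baseline, end of treatment) as the within subject factor, and a group by time interaction". Baseline is therefore a response, with its own mean in each arm. The primary hypothesis is the group-by-time contrast between BFP and Cogpack. Further contrasts are to be used "to examine the magnitudes of group differences at the end of treatment". The model is justified thus: "To make the most efficient use of our data, our primary analytical technique will be the general linear mixed model".

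Covariate-by-time terms appear only under Exploratory Analyses, for a list of possible moderators: "we will also add these measures and their interactions with treatment group and time to the primary models". No baseline-adjusted primary analysis is specified anywhere.

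**The concern.** There are two linked issues.

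- **The rule does not act on the primary contrast.** A covariate entered as a main effect shifts a subject's baseline and endpoint scores equally, so it drops out of the change. If one arm starts worse by chance on a primary outcome, part of its regression to the mean is read as training gain, and the rule leaves that in place. If a time interaction was intended, the plan needs to say so, because that choice does change the estimate.
- **Precision is lost regardless of imbalance.** Randomisation makes the true baseline means equal. A model that estimates them separately discards that information.

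The second issue is the larger one. It touches all three primary outcomes and every between-arm contrast, in a study described this way: "since this is a preliminary study, designed to obtain estimates of treatment effects".

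**Working it through.** **Inputs.** From Power Considerations: r = .7, two-sided alpha .05, d = 0 at baseline and .5 after treatment, 48/48/24 enrolled. From Randomization and Treatment Procedure: 20% attrition, leaving 38/38/19. Assumptions: SD 1 at both visits (the plan gives no SDs) and loss at endpoint only, so .8 × 48 = 38.4 and .8 × 24 = 19.2 have an endpoint.

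**1. The plan's own figure.** With two visits and complete data, group-by-time is a comparison of change scores with SD √(2(1−r)) = √.60 = .775. With 38 per arm, power for d = .5 is 80.3% (normal) or 79.3% (noncentral t). The plan says only that power is sufficient; 80% is taken from the neighbouring sentences. On that reading the figure reproduces.

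**2. Main-effect covariates.** In one simulated complete data set with an imbalanced covariate, the contrast was −0.338 (SE 0.184) without it. It was identical with the covariate as a main effect, and identical with the baseline outcome as a main effect. It moved to −0.209 (SE 0.176) only when covariate-by-time was added. In a second data set, with 20% of endpoints missing, a main effect moved the contrast from −0.3246 to −0.3239, and covariate-by-time moved it to −0.161. Over 2,000 simulated trials the core and main-effect estimates were identical without loss. With 20% loss they differed by .013 on average and .09 at most.

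**3. Precision, BFP against Cogpack, all available data.**

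- Core: 2[(1−r²)/38.4 + (1−r)²/48] = 2[.51/38.4 + .09/48] = .0303, SE .1741.
- Common baseline mean: 2(1−r²)/38.4 = 2(.51/38.4) = .0266, SE .1630.
- Variance ratio .876, a 12% saving. With complete data it is .51/.60 = .85, a 15% saving.
- Power for d = .5 (noncentral t, 93 df): 81.1% to 85.9%. For 38 completers per arm: 79.3% to 85.3%.
- Each active arm against control (48 v 24, 20% loss): SE .213 to .200. Power for an assumed d = .5: 64% to 70%.
- Variance ratio with 20% loss: .789 at r = .5 and .960 at r = .9.

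If the endpoint SD is k times the baseline SD, the complete-data saving is (1−rk)²/(k² + 1 − 2rk), which is never negative. At r = .7 it is 25% for k = 0.9, 8% for k = 1.1 and 3% for k = 1.2.

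**4. Trials with a significant baseline difference on the outcome itself.** The change contrast shifts by −(1−r) = −.30 per SD of baseline imbalance. Among trials with a significant three-group baseline ANOVA (5.0% of trials), the mean BFP-Cogpack gap was .362 SD, so the expected bias is .30 × .362 = .11 SD. REML simulations used 4,000 such trials per row, 48/48/24, 20% random loss and compound symmetry (an assumption; the plan names no covariance structure):

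| r | Bias, core (SD) | Type I, core | Type I, baseline outcome as main effect | Type I, common baseline |
|---|---|---|---|---|
| .5 | .176 | .117 | .159 | .050 |
| .7 | .104 | .087 | .126 | .052 |
| .9 | .034 | .063 | .097 | .046 |

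At r = .7 the main effect leaves the bias at .103 while the SE falls from .173 to .156, so type I error rises. Two further sets of runs at r = .7 (8,000 and 6,660 trials) gave .097 and .088 for the core model and .133 and .126 with the main effect.

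**5. Over all trials.** The rule adds about .05 × (.126 − .087) = .002 to type I error, from about 5.0% to 5.2%.

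**6. The end-of-treatment difference (r = .7, 20% loss).** For another imbalanced covariate correlated .4 with the outcome at both visits (assumed), the rule reduces bias from .139 to −.007 and type I error from .091 to .048. The group-by-time contrast needed no correction there (bias .004, type I .047). A common baseline alone left a bias of .04 SD in size, with type I error .052. With the outcome's own baseline as a main effect, endpoint bias went from .259 to −.055, but type I error only from .217 to .201, because near-zero baseline residuals pull the pooled SE down to .114.

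**The case against.** The strongest reply is that nothing here is an error. The group-by-time mixed model is a legitimate prespecified analysis, it matches the powered contrast, and overall type I error hardly moves. All of that stands.

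The main-effect reading is also not in the text. Entered with a time term, or as an ANCOVA covariate, an imbalanced baseline outcome would be handled properly. That is true, and it is why the criticism is conditional. The plan still has to say which form it means.

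For the seven measures that are not outcomes, the simulated case showed no bias in the primary contrast, and the rule did repair the end-of-treatment difference. This stands too. Bias in the primary contrast would require such a measure to predict change, and the documents give no value for that. The conditional bias is likewise a property of any change contrast, confined to about 5% of trials per outcome.

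The 12% and 15% savings rest on equal SDs, which the plan does not state. The plan's own d = .5 figure reproduces under that assumption, and the saving only shrinks or grows at other ratios; it does not reverse. The efficiency claim in Primary Analyses can fairly be read as being about repeated measures and missing data. Even so, a more precise model of the same kind uses the same data.

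Finally, endpoint ANCOVA drops subjects who lack either visit, against the stated aim: "This allows us to include all available data from all subjects in the analyses". That favours the common-baseline mixed model, which keeps them.

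**Conclusion.** The point holds as a free improvement that should be made; the planned test is not invalid. The main cost of the present plan is precision. At r = .7 with equal SDs, the BFP-Cogpack contrast carries avoidable variance (12% with 20% endpoint loss, 15% with complete data), worth about five to six points of power at d = .5. The gain is larger at lower r and small near r = .9.

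The secondary cost is that the covariate rule, if it means main effects, leaves the primary contrast uncorrected when a primary outcome is itself imbalanced. The bias is then about 0.11 SD. Type I error in those trials is 8–10% for the core model, 12–13% with the baseline outcome as a main effect, and about 5% with a common baseline. These conditional figures assume compound symmetry and random loss.

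**What to change.** For each primary outcome, replace the significance-triggered rule with one prespecified baseline-adjusted analysis. The mixed model with a common baseline mean across arms fits the plan best, because it keeps all available data; endpoint ANCOVA on the baseline value is the alternative. State the covariance structure. Name any other adjusters in advance and enter them with a covariate-by-time term (or as covariates in the ANCOVA), since a common baseline for the outcome does not by itself deal with imbalance in other measures. Keep the baseline comparisons as description only.

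The cost is a change of SAP wording. Baseline is already collected, the same mixed-model software serves, and no patients or visits are added.
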